8 BACKGROUND INFORMATION AND RATIONALE

8.1 Lung transplantation in the United Kingdom

Approximately 4300 organs are transplanted per year in the UK; 200 of these are lung transplants(1). Immunological rejection of the transplanted organ is one of the biggest hurdles in transplantation. Patients require life-long immunosuppression to reduce the risk of rejection. Current immunosuppressive regimens are less than ideal. They are non-personalised, require lifelong use, can damage the transplanted tissues and significantly increase morbidity and mortality by increasing the risk of infections (viral -up to 50% of recipients, fungal-up to 59% of recipients, and often multi-drug resistance bacterial infections -up to 45% of patients). They also increase the risk of malignancies, including lymphoproliferative disorders (up to 20%), increasing the risk of cardiovascular disease, hypertension, kidney failure and diabetes, resulting in a significant reduction in life expectancy. Life expectancy for lung transplant patients has remained unchanged in the last 15 years. Survival is currently ~80% at 1-year and decreases to 35% at 10-years, mainly due to organ rejection and immuno-suppression associated morbidity(2).

Despite immunosuppression, acute cellular rejection (ACR) is prevalent in the first year, affecting ~30-80% of lung transplant recipients(3). ACR must be detected and treated to prevent loss of the organ. However, the symptoms are non-specific, consisting of inflammatory organ dysfunction and often occur late in the ACR process. Consequently, the early diagnosis of ACR is very difficult and usually made by excluding other causes of inflammation by biochemical, imaging and histological tests. Weekly to monthly organ biopsies are often performed to exclude asymptomatic milder forms of rejection during the first year.

Apart from the threat of immediate loss of the transplanted organ, the number, severity and duration of ACR events significantly increases the longer-term risk of organ fibrosis, chronic rejection, loss of function, organ failure and death. Therefore, early diagnosis and treatment of rejection is critical. This will prevent and minimise organ injury from the immune response, prolong organ function, and minimise immunosuppression morbidity.

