- 4. disease or disorder being studied, or sign or symptom associated with the disease or disorder unless more severe than expected for the participant's condition;
- 5. overdose of concurrent medication without any signs or symptoms

Seriousness vs severity

A distinction is drawn between serious and severe AEs. Severity is a measure of intensity whereas seriousness is defined using the criteria above. Hence, a severe AE need not necessarily be serious.

19.3 Reporting of Serious Adverse Events (SAEs) from sites to the central study team

Only serious adverse events considered by to be related (possibly, probably or definitely) to any of the study procedures will be reported to the central study team. Such events must be reported within 24 hours to the central study team using the SAE form within the REDCap study database. On notification/receipt of an SAE the central study team will perform an initial check of the report and request any additional information from the site team. The SAE will be assessed by the CI for relatedness (see 19.5). The SAE will also be reviewed by the Nominated Person for the trial, who will perform the assessment of expectendess, according to section 19.4.

The **Surgical complications** listed below should not be reported on a SAE form unless the complication is (in the opinion of the CI or designee) considered more severe in nature than might be expected, or unexpected, for the particular intervention received.

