19.4 Surgical complications

The following treatment-related complications will be collected on the peri- and postoperative complications case report forms (CRFs) and should not be reported separately on a SAE form unless the complication is (in the opinion of the site investigator) considered more severe in nature than might be expected, or unexpected, for the particular intervention received by the participant.

Peri-operative complications (events occurring intraoperatively, during the immediate post-operative period, or in the first 14 days post-procedure):

Skin Flap:

- Bleeding/Haematoma
- Wound dehiscence
- Infection (spreading wound inflammation, purulent discharge requiring additional antibiotics)
- Arterial supply problem to the flap
- Venous supply problem to the flap
- Vascular supply deficiency
- Nerve supply to hand (numbness, paraesthesia, weakness, paralysis, palsy, stiffness, carpal tunnel syndrome)
- Delayed wound healing
- Flap necrosis: partial %/total

Lung Transplant:

- Pneumothorax
- Haemothorax
- Bleeding/Haematoma
- Wound dehiscence
- Wound Infection (spreading wound inflammation, purulent discharge requiring additional antibiotics)
- Empyema

- Vascular supply problem to the lung transplant
- Delayed wound healing
- Air leaks
- Bronchial anastamotic leak
- Bronchial stenosis
- Bronchial malacia
- Infection- cmv/other respiratory virus/aspergillus/mycobacterial/other
- Cryptogenic organising pneumonia
- Pulmonary embolism
- Pulmonary infarction

Post-Operative: Events occurring at any time during follow-up period likely related to a study intervention: (3 - 12 months) *from 2 weeks.

Skin Flap:

- Nerve supply to hand (numbness, paraesthesia, weakness, paralysis, palsy, stiffness, Carpal tunnel syndrome)*
- Infection (spreading wound inflammation, purulent discharge requiring additional antibiotics)*
- Arterial supply problem to the flap*
- Venous supply problem to the flap*
- Flap necrosis*
- Vascular supply deficiency
- Pain
- Tendon dysfunction

Lung Transplant:

- Bronchial dehiscence*
- Bronchial stenosis
- Bronchial malacia
- Infection- cmv/other respiratory virus/aspergillus/mycobacterial/other
- Cryptogenic organising pneumonia
- Pulmonary embolism
- Pulmonary infarction
- PTLD (post transplant lymphoproliferative disorder)
- GVHD (graft versus host disease)
- Chronic rejection
- Upper lobe fibrosis
- Post trans-bronchial biopsy related complications
- Bronchogenic carcinoma

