24.2 Sample Size/Power calculations

The anticipated 12-month rejection rates for lungs in the control arm by 12 months is 80%. Published rates vary between 33-100% (43–46) depending on definition and grade of rejection and method of analysis. However, a comprehensive study of regular transbronchial biopsies in 299 lung transplant patients showed a cumulative incidence of rejection (≥grade A1) of 91.7% in the first 12 months and (≥grade A2) of 77.9% (46).

In the SSF intestinal study, we observed a 72% reduction in biopsy-proven acute rejections from the 77% rejection rate in the control arm reducing to 22% in the with skin arm. However, as a more conservative estimate for this study, we consider a relative reduction of a third from 80% to 53.33% (corresponding to an absolute difference of 26.67%) to be clinically meaningful. 128 participants who have had a transplant are required for the analysis to achieve 90% power at a two-sided significance level of 5%. To allow for a 15% loss to follow-up or death by 12 months (76 per trial arm) 152 participants need to have been randomised and transplanted. In total, approximately 254 randomisations will be required to achieve this number and account for participants not proceeding with transplant.

Assessment of the diagnostic accuracy of the SSF compared to the current reference standard (organ biopsy) is a secondary objective of this study, and is undertaken in participants who received an SSF. Assuming approximately 80% specificity, and 90% specificity, based on previous studies, 95% confidence intervals (Wilson method) around the sensitivity, specificity, positive and negative predicted values will have a width of approximately 20-30%, depending on the observed sensitivity, specificity and event rates. A sample size of 64 participants receiving SSF and providing one-year follow-up data, an expected rejection rate of 53%, and anticipated values of 80% and 90% for sensitivity and specificity, respectively, will provide approximately 80% power (at a one-sided 5% significance level) to show that the observed sensitivity and specificity in the study are statistically significantly higher than 60% and 70%, respectively.

Since the proposed mechanistic sub-studies are intended to be hypothesis generating, no formal sample size calculations have been performed.

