24.3 Choice of primary outcome

The primary outcome is lung rejection events in the first 12 months post randomisation. This is the common reporting period and the period in which the majority (90%) of first rejection events occur. After this period, the transplant is immunologically more stable. Although there is a correlation between rejection episodes and transplant organ loss and mortality, in order to demonstrate that reduced rejection events do translate into improved patient and organ survival, longer-term patient and transplanted organ survival and functional data will be analysed for 5 years, as part of a separate longer term study subject to funding. AE and SAE data will also be collected over this period. The data is already routinely collected by the transplant units and reported to NHSBT annually.

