24.6 Secondary outcomes

For diagnostic accuracy of the first test taken, proportions of observed true positives, true negatives, false positives and false negatives will be presented. Estimates of sensitivity, specificity, positive and negative predictive values will be generated, as well as the positive and negative likelihood ratios together with corresponding 95% confidence intervals, using the Wilson method. Diagnostic accuracy will be calculated for rejection events diagnosed by both methods (biopsy and clinical) for the entire trial period. A sensitivity analysis will include data for the first three months of patient follow up (to which point all suspected rejections are diagnosed using biopsy). Skin flap rejection events, by severity, will be summarised descriptively. Time to first skin flap rejection, transplanted lung and patient survival will be analysed following the methods used for the primary outcome. Competing risks will be considered if the number of deaths not related to the transplanted organ is sufficiently high to warrant such analyses. Transplant lung function (vital capacity, forced expiratory volume) will be analysed using mixed-effects linear regression models, including treatment, and adjusted for centre as a random effect. Development of de-novo specific antibodies, development of graft versus host disease, and evidence of chronic rejection, will be analysed using a mixed-effects logistic regression model, including treatment, and adjusted for centre as a random effect. Safety events (AEs, SAEs, complications), immunosuppressive levels (and requirements) and immunological markers will be summarised descriptively. HRQoL outcomes will be analysed using mixed-effects linear regression model, including treatment and adjusted centre and patient as random effects. Supplementary analyses of HRQoL will also use the area under the curve statistics.

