24.13 Level of Statistical Significance

All principal analyses will be performed at the 2-sided 5% significance level.

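### Section 24.6 promises an AE summary, but sections 17.3 and 19 collect only listed complications and related SAEs, so several harms that 8.1 names cannot be compared between arms

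*Protocol*

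**What the plan says.** Section 24.6 sets out the safety analysis: "Safety events (AEs, SAEs, complications), immunosuppressive levels (and requirements) and immunological markers will be summarised descriptively". Section 24.4 adds that outcomes collected in both arms are split by treatment group. Section 24.9 defines a safety population grouped by whether a skin transplant was received.

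The collection rules are narrower:

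- Section 19.2 defines an AE at length but does not tell sites to record AEs in general.
- Section 19.3 limits SAEs: "Only serious adverse events considered by to be related (possibly, probably or definitely) to any of the study procedures will be reported" to the central team.
- Section 19.4 opens its flap and lung lists thus: "The following treatment-related complications will be collected on the peri- and postoperative complications case report forms (CRFs". Section 20 sends expected events to the same forms, and section 19.1 says complications are recorded in both groups.
- The 3-, 6- and 12-month tables in section 17.3 cover flap complications, rejection, transplant function, immunosuppression and survival, with antibodies at 3 months. None has an AE item. Co-morbidities are collected at baseline only.
- Table 3 has one general row for clinical outcome data, without fields.

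Section 8.1 describes the harms of immunosuppression as infections, malignancies including lymphoproliferative disorders, and "increasing the risk of cardiovascular disease, hypertension, kidney failure and diabetes".

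**The concern.** Taken at its word, 24.6 calls for a table that nothing in sections 17.3 or 19 feeds. A non-serious event that is not on the 19.4 list has no stated route to the database. Nor does a serious, unlisted event that the team judges unrelated, unless it is fatal and so counts under survival.

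This matters because the unlisted harms bear on the trial's own argument. Sections 8.1 and 8.7 present less immunosuppression morbidity as a hoped-for benefit. Section 16.10 says flap rejection is usually treated with methylprednisolone, with escalation of immunosuppression if required and at local discretion. Harms of immunosuppression could therefore fall or rise in the flap arm. Section 16.11 records the immunosuppression given, but not these consequences of it. The trial could then neither support the claimed reduction nor notice an increase.

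**Working it through.** **The plan's own figures.** The protocol gives no figure for safety events. Its sample size does reproduce. With 80% v 53.33%, two-sided 5% and 90% power, the pooled-variance formula is n = [1.960·√(2·0.6667·0.3333) + 1.282·√(0.80·0.20 + 0.5333·0.4667)]² / 0.2667² = 63.6. That rounds up to 64 per arm, or 128. Then 64/0.85 = 75.3, so 76 per arm, or 152. The present point does not depend on these figures except for the arm size of 76.

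**Harms named in 8.1 against the list in 19.4.**

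| Harm in 8.1 | On the 19.4 lung list (both arms)? |
|---|---|
| Infection (viral, fungal, bacterial) | Yes, with an open category for other organisms |
| Lymphoproliferative disorder | Yes (PTLD) |
| Other malignancy | Only bronchogenic carcinoma |
| Cardiovascular disease | No |
| Hypertension | No |
| Kidney failure | No |
| Diabetes | No |

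So 2 of 7 are listed, 1 is partly listed and 4 are not (2 + 1 + 4 = 7).

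**Does SAE reporting fill the gap?** It does so only for events that are serious and judged related. Section 19.3 refers to study procedures, 19.5 assesses relatedness to the study intervention, and 19.6 identifies that intervention as the skin flap. Control participants have no flap, so few of their events can qualify on that reading. Section 15.7 says site staff are not blinded. SAE counts could therefore differ between arms because of the filter alone.

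**How complete is capture of the listed harms?** Section 19.4 has a peri-operative list for the first 14 days. Its post-operative list takes events thought likely to stem from a study intervention, at 3 to 12 months, with starred items counted from 2 weeks. Lung infection is on both lists but is not starred on the second. Read literally, 2 weeks to 3 months is uncovered: about 13 − 2 = 11 weeks. PTLD and bronchogenic carcinoma are only on the post-operative list, unstarred. The same heading also speaks of any time during follow-up, so the text is at odds with itself. The follow-up tables in 17.3 name only complications of the flap.

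**Exposure.** Section 8.4 reports flap rejection in under 25% of earlier flap recipients. If that carried over, at most 76 × 0.25 = 19 flap participants would have flap rejection. Because treatment is discretionary, 19 is also an upper bound on those given steroids for it.

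**Precision if the events were recorded.** The protocol gives no rates for the unlisted harms, so I assume a common rate p in both arms and 76 with data per arm. The 95% half-width for a difference is 1.96·√(2p(1−p)/76). At p = 0.10 this is 1.96 × 0.0487 = 0.095, and at p = 0.50 it is 1.96 × 0.0811 = 0.159. Comparisons would be good to about ±10 to ±16 percentage points.

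**The case against.** The strongest reply is that this is loose labelling. Section 24.9 attaches the term safety events to secondary outcome 2d, the surgical and flap complications. The AEs in 24.6 may mean no more than that. Secondary objective 2 has items a to g, none of them renal, metabolic or cardiovascular, and less immunosuppression morbidity is rationale rather than an endpoint. On this view the new fields extend the trial instead of correcting it. This stands in part: the necessary correction is to reconcile 24.6 with section 19, and the added fields are an improvement. It does not remove the mismatch, since 24.6 names AEs beside SAEs and complications and 19.2 defines them separately.

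It may also be said that the CRFs are not shown and that a statistical analysis plan may say more. The CRFs could hold further fields, so the absence of a route is an inference from the protocol's lists. But an analysis plan cannot summarise data that were not collected, and the protocol text would still need reconciling.

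Three stronger readings are tempting and are not supported:

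- A reader might infer that none of the immunosuppression harms in 8.1 can be compared. Infection and PTLD, the harms for which 8.1 gives rates, are listed for both arms, as is bronchogenic carcinoma.
- A reader might take the statement in 24.3, "AE and SAE data will also be collected over this period", as a promise for this trial. It refers to a separate 5-year study that depends on funding.
- A reader might infer that the trial would report no difference in harms it did not record. Section 24.6 plans descriptive summaries, so those harms would simply go unreported.

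**Conclusion.** The point holds in a limited form. The AE summary in 24.6 has no stated data source beyond listed complications and related SAEs. Four of the seven categories of harm in 8.1 (kidney failure, diabetes, hypertension and cardiovascular disease) cannot be compared between arms. Nor can malignancy other than PTLD and bronchogenic carcinoma. The harms that are listed are captured incompletely, through a relatedness filter applied without blinding and, read literally, with a gap of about 11 weeks for lung infection.

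The clinical size of what would be missed cannot be stated from the documents. The primary outcome and the sample size are unaffected. The conclusion assumes that the CRFs follow the lists in 17.3 and 19.4. If they already hold the missing fields, only the wording needs correcting.

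**What to change.** 1. In 24.6, replace the general reference to AEs with the events actually collected, so that it agrees with section 19. Section 24.3 needs no change.
2. In 19.4, reconcile the post-operative time window with its own heading, so that it is clear whether lung infection, PTLD and bronchogenic carcinoma are recorded between 2 weeks and 3 months.
3. Add a short list to the existing 3-, 6- and 12-month CRFs, in both arms and regardless of relatedness, taken from routine notes: kidney function, new diabetes, new hypertension or cardiovascular event, treated infection over the whole of follow-up, and any malignancy.
4. Report counts by arm with 95% CIs, as description and not as tests.

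The cost is a few CRF fields, slightly more data entry and a small text edit. No new visit or test is needed: section 17.1 already lists renal function among the usual investigations, and trial follow-up coincides with routine clinics. The change is best made before follow-up begins, because even ascertainment across arms would be hard to recover afterwards.

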The technique is called a sentinel skin flap (SSF) transplant. This involves transplanting a small patch of skin from the same donor onto the arm of the patient at the same time they receive the organ transplant. Skin seems to reject earlier than other organs and is easily visible. If rejection develops, a rash appears on the skin. Medical professionals can then treat the rejection as soon as the rash appears, to try to prevent the organ also rejecting. The researchers conducting this studyhave tested this technique for some other solid organ transplants such as pancreas transplants for diabetes, and intestine transplants. We have found that this skin rash indicates rejection much more quickly than were we to rely solely on the intermittent standard tests. Additionally, rather than having invasive tests every week or so, patients can just look at the skin everyday to check for a rash. This study is to check if the flaps do or do not do the same things in individuals who have a lung transplant.

This study is being conducted to see if a small piece of skin attached at the same time as a lung transplant can act as a rejection monitor for lung transplants. This could then potentially avoid the regular tests and hospital visits, reduce the immune suppression drug levels, and avoid rejection injury to the transplanted lung. We need 152 adults who have a lung transplant from the five NHS lung transplant hospitals in England to know if the skin attachment does or does not work as a rejection monitor.

Participants who agree to take part in this study, and who then are matched with a lung donor as part of the standard NHSBT allocation, if the donor/donor family has also consented to the giving of some skin and lungs, will be randomly allocated to receive either a lung transplant alone, or a lung transplant with a flap of skin transplanted from the same donor at the time of their offer of a transplant.

The skin transplant will be a small patch (eye-shaped and approximately 10x3 cm, which is about the size of two fingers together) of skin attached ideally to the under surface of the forearm. Participants will be taught to examine the skin for signs of a rejection rash. If such a rash is seen, a tiny biopsy from the skin will be taken to confirm the presence of rejection. Apart from the addition of the skin patch (flap) transplant, all other treatment, visits and care will be the same. Participants will come back to clinic for their usual follow-up visits.

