8.5 Safety issues of skin and solid organ transplantation

The high frequency of rejection in skin bearing a VCA raised concerns that adding a skin flap VCA transplant to the SOT would increase rejection events or require increased immunosuppression. We found that not only did this not occur, conversely, the overall rejection rate (skin +SOT) was less than expected compared to SOT alone or skin flap VCA alone. This suggests that combining the transplants confers some immune-protection(11). We were also concerned that the addition of skin flap VCA may increase the development of antibodies against the transplants, resulting in increased antibody mediated rejection, chronic rejection associated fibrosis and vascular occlusion. However, we found no such increase in the development of donor-specific antibodies or chronic rejection features (37).

The few reports of skin transplants and SOT showed that combination transplants of this nature were safe (17).

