8.7 Why this research is needed now

A review of research priority setting in transplantation (40) identified the following priorities, which are targeted in this study:

- 1. Optimizing and individualising regimens to improve outcomes;
- 2. Developing ways to assess response to therapy including surrogate marker(s) for adequacy of immunosuppression;
- 3. Improving strategies for monitoring the level of immunosuppression; and
- 4. Reducing the need for immunosuppression.

Adopting SSFs into routine transplant practice would greatly reduce the demands of follow-up, which is currently weekly visits for 3 months, then blood and other tests every 6 weeks, and 3-monthly visits for life. In our previous studies, the skin flap led to significant changes in clinical practice after the first year, with patient self-monitoring, reducing the need for regular endoscopy and organ biopsy (38).

Patients may benefit from being able to self-monitor their immunological status, titrate and reduce their suppression dosing. This reduces the associated morbidity, reduces their hospital visits and the number of interventions and tests. It may result in better organ function and longer organ survival, with increased psychological well-being at being able to reassure themselves, better self-control and involvement in their health.

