		specific antibodies ¹	randomisation		
		f. Development of	Events up to 12	Diagnosis of graft versus	Participant's medical
		graft versus host	months post	host disease	notes
		disease ¹	randomisation		
		g. Evidence of	12 months post	Chronic rejection	Histology report
		chronic rejection in	randomisation	S. A SING TOJOCKION	
		lung ¹	Tanaomisadon		
3	To establish if the	Immunosuppression	Events up to 12	Number and type of	Prescription for
٥.	addition of a	levels and	months post	immunosuppressants	immunosuppressants
	sentinel skin flap	requirements ¹	randomisation	given and target levels	Immunosuppressants
		requirements	randomisation		
	changes the			/doses (steroid,	
	immunosuppressio			mycophenolate mofetil	
	n requirements			(MMF), tacrolimus,	
_	-		B 11 0 1 1 2	others);	5
4.	To establish if		Baseline, 3 and 12	SF-36; EQ-5D-5L; DAS-24	
	being able to	by the following	months post		outcome measure
	personally check	validated	randomisation		
	on immune	questionnaires: SF-			
	response/rejection	36; EQ-5D-5L and			
	of transplant	DAS-24 ¹			
1					

changes quality of		
life, or if rendering		
the transplant		
visible adversely		
effects QoL		

¹ Outcome assessed in both intervention and comparator;

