16.11 Immunosuppression following transplantation

Immunosuppression will be managed by the healthcare team according to standard practice at the participating transplant centre. Maintenance immunosuppression will be changed at the discretion of the clinical team according to factors such as serum levels, rejection episodes, renal function, neutrophil count, viral infections and side effects. Details of the immunosuppression and changes to the immune-suppression regimen that the participant receives will be collected on the case report form.

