24.4 Description of Statistical Methods

Results will be reported in line with the CONSORT statement and relevant extensions (41)(42).

All outcomes will be summarised using descriptive statistics overall and, when collected for both arms, split by treatment groups. Binary and categorical data will be summarised by frequencies and percentages. Continuous data will be summarised by means and standard deviations (SDs), or median and inter-quartile range if data are skewed. Corresponding 95% confidence intervals will be presented where possible. Visual representation of outcomes will be considered and, where it will support interpretation, presented.

Analysis will be conducted using a complete case approach, no imputation methods for missing data are planned. Analysis of the primary and secondary outcomes will be done once the 12 month follow up has been reached by the last patient. Analyses of these outcomes will be pre-specified in a statistical analysis plan finalised prior to un-blinding of the data. Analysis of mechanistic outcomes, using sample data, will be done following completion of the primary and secondary outcomes.

An independent Data and Safety Monitoring Committee (DSMC) will meet early in the trial to agree its terms of references. They will review confidential interim analyses of accumulating data, including the interim analysis of the stop-go criteria and diagnostic accuracy.

It is anticipated that all statistical analysis will be undertaken using Stata (StataCorp LP, www.stata.com) or other well validated statistical software.

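### Secondary objective 3 asks whether the flap changes immunosuppression requirements, but the protocol commits to no between-arm difference that would answer it

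*Protocol*

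**What the plan says.** Protocol 9.3 sets secondary objective 3: to establish whether the addition of the flap changes the immunosuppression a recipient needs. The data listed are the number and type of immunosuppressants and their target levels or doses (steroid, mycophenolate mofetil, tacrolimus, others), over the 12 months after randomisation. The footnote attached to this outcome reads "Outcome assessed in both intervention and comparator".

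The analysis is fixed in 24.6: "immunosuppressive levels (and requirements) and immunological markers will be summarised descriptively". The general rule in 24.4 is "All outcomes will be summarised using descriptive statistics overall and, when collected for both arms, split by treatment groups", followed by "Corresponding 95% confidence intervals will be presented where possible".

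The same paragraph of 24.6 gives lung function a mixed-effects linear model. De-novo antibodies, graft versus host disease and chronic rejection get a mixed-effects logistic model, and quality of life a mixed-effects linear model. Each includes treatment, with centre as a random effect.

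On why the question matters, 8.7 lists "Reducing the need for immunosuppression" among the research priorities that the trial addresses. The lay summary says the flap might eventually "reduce the immune suppression drug levels". Section 8.5 records the opposite worry, that adding a flap "would increase rejection events or require increased immunosuppression", and reports that the group's earlier experience did not bear it out. On conduct, 16.11 states: "Immunosuppression will be managed by the healthcare team according to standard practice at the participating transplant centre".

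**The concern.** Whether the flap changes requirements is a question about a contrast between arms. The trial randomises, collects the data in both arms, and already applies intention-to-treat by allocated arm to the secondary outcomes other than 2d (24.9). Yet an analyst who follows 24.6 and 24.4 to the letter would produce two columns of summaries and no estimate of the difference.

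This is a method that the protocol states for a named outcome, so it is not simply a detail awaiting the SAP.

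The direction of any effect is open. The flap is hoped to allow less immunosuppression. It also brings its own reason to treat: 16.10 describes intravenous methylprednisolone as usual for biopsy-proven flap rejection, with escalation of daily immunosuppression if required. If the two columns look alike, they could be read as showing no increase, with no interval to say how large an increase remains compatible with the data.

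**Working it through.** **1. Objective against analysis.** The outcomes in 9.3 and their analysis in 24.6 compare as follows:

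| Outcome | Analysis in 24.6 |
|---|---|
| Lung function (2c) | Linear mixed model with treatment; centre random |
| De-novo antibodies (2e), graft versus host disease (2f), chronic rejection (2g) | Logistic mixed model with treatment; centre random |
| Quality of life (4) | Linear mixed model with treatment; centre and patient random |
| Complications (2d) | Descriptive |
| Immunosuppression (3) | Descriptive |

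Complications are the other descriptive entry. Most of the flap complications can arise only in flap recipients, so a descriptive report is natural there. Outcome 3 is worded as a comparison and measured alike in both arms.

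**2. Does another section supply the contrast?**
- 24.4 gives by-arm summaries with intervals where possible. It names no difference.
- 24.7 says that its intervals are meant to support simple group comparisons, but it covers the mechanistic outcomes only.
- 24.8 plans a recurrent-event model for lung or skin rejection events. That counts rejections, not drugs, doses or levels.

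None of these commits to a difference for outcome 3.

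**3. The plan's own sample size, to fix the analysed number.** Inputs from 24.2: 80% against 53.33%, two-sided 5%, 90% power. The mean proportion is 0.6667 and the difference 0.2667.

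n per arm = [1.96 × √(2 × 0.6667 × 0.3333) + 1.2816 × √(0.80 × 0.20 + 0.5333 × 0.4667)]² / 0.2667²
= (1.307 + 0.819)² / 0.0711 ≈ 63.6, so 64 per arm and 128 in total.

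With 15% loss, 64 / 0.85 = 75.3, so 76 per arm and 152 in total. Both stated figures reproduce.

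**4. What an estimated difference would deliver.** Take a continuous measure such as a dose or level, with 64 per arm and a normal approximation. The protocol gives no standard deviation, so results stay in SD units.

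- 95% CI half-width of the unadjusted difference in means: 1.96 × √(2/64) = 0.346 SD.
- If all 76 per arm contributed: 1.96 × √(2/76) = 0.318 SD.

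An observed difference of exactly zero would therefore still leave about 0.35 SD in either direction inside the interval. This is the information that the planned summaries do not report directly. Because immunosuppression follows each centre's own practice (16.11) and randomisation is stratified by centre for differences in routine practice (15.4), adjusting for centre could narrow the interval. The documents give no basis for saying by how much.

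**The case against.** There is a fair case for leaving the text alone.

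- **The SAP can add a difference.** Section 24 is presented as a summary, with details to follow in the SAP. Nothing in 24.6 forbids a contrast, and the intervals in 24.4 are not expressly limited to single-arm quantities. This stands. A reader might infer that the protocol rules out a comparison, or that none will ever be estimated. The text supports only the narrower statement that the protocol does not commit to one.
- **The outcome is not one variable.** Several drugs, target levels and doses offer no obvious single estimand, whereas lung function and quality of life have defined scales and antibodies are present or absent. Clinicians change maintenance therapy for renal function, neutrophil counts, infection and side effects (16.11), and no flap-guided reduction is mandated. This stands as a reason to keep most of the detail descriptive. It does not explain why no single measure, such as the number of agents or the steroid dose, is compared.
- **The stakes are modest.** The lay-summary phrase is a hope for later practice, and 8.7 places the earlier changes in clinical practice after the first year, beyond this trial's follow-up. This also stands. The concern in 8.5 about increased requirements nevertheless falls within the trial period.

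A further tempting step is to put a number on how badly readers would be misled by comparing the by-arm intervals, or to project counts of anti-rejection courses. The documents support neither. The protocol states no rule for reading the intervals against each other, and it gives no rate of flap rejection in lung recipients from which to project courses.

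**Conclusion.** The point holds as a minor mismatch between an objective and its analysis. Objective 3 is comparative and measured in both arms, and the protocol commits only to by-arm description, with intervals where possible. It does not follow that the objective is unanswerable or that a comparison is excluded: the data will exist and an informal side-by-side reading will be available.

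The only size that can be given is the precision of the missing estimate, about 0.35 SD either side for an unadjusted difference in means. This assumes a roughly normal continuous measure and that the 128 participants planned for the primary analysis also provide it. The primary outcome, sample size and safety analysis are unaffected.

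**What to change.** In 24.6, take immunosuppression requirements out of the descriptive-only sentence and add wording such as:

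*For one or two measures of immunosuppression requirement at 12 months (for example, the number of maintenance immunosuppressants, and the steroid dose or tacrolimus target level), the between-arm difference and its 95% confidence interval will be estimated by allocated arm, with centre as a random effect. No formal test will be made. Other drugs and levels will be summarised by arm.*

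The measures should come from the data that outcome 3 already lists. Courses of anti-rejection treatment, whether triggered by skin or lung, may be added as a supplementary estimate, since treatment and its date are already recorded (16.10, 17.3).

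The cost is one or two sentences, a little derivation work and one or two more secondary estimates. No new data collection and no change to the sample size are needed. Steroid dose may be only partly derivable from what is recorded, so the SAP should confirm which measure is complete enough to use.
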